10.7 Risk/Benefit Assessment

Potential Study Risks

For trial participants (Aim 1), there are potential physical risks to the patients. These include:

- Incorrect medication adherence information given to the patient through text messages
- Incorrect symptom management information given to the patient through text messages
- Incorrect alerts to the patient's care team based on text message information
- HIPAA concerns related to text messaging
- Non-study personnel having access to the PHI of patients, specifically through the texting interactions on a patient's mobile device or through a security breach on the program platform
- Discomfort with disclosing information in the online surveys

Patients will be made aware of these risks during the informed consent process, will be informed that study investigators will be monitoring all interactions between the patient and Penny, reminded that Penny should not be used for emergency situations, and will be encouraged to ask questions.

For interview participants (Aim 2), potential risks to participating in this study include: potential violation of confidentiality or privacy; possible discomfort in disclosing information on screening knowledge, beliefs or practices; and possible concern among providers or employees that participation will negatively impact job or clinic performance or evaluation. These risks will be outlined in the interview consent form (to be submitted for review prior to commencement of interviews).

Potential Study Benefits

For trial participants (Aim 1), there are potential study benefits to the patients and society. These include:

- Easing the process of adherence to a patient's oral therapy regimen
- Real time feedback on side effects and symptoms for the patient
- Improved communication for the patient with their care team
- Potential to improve the quality of life for the patients
- Potential to improve the outcome of an oncology diagnosis and its treatment
- Potential reduction in costs associated with a patient's oncology-related medical care if ED visits, admissions and side effects are prevented and/or managed sooner
- If the study is successful, expanding to use in more disease states within oncology to provide benefit to future patients

For interview participants (Aim 2), there are no direct benefits who participate in the interview component of this study. However, they may indirectly benefit by discussing experience and practices. For the health of society, the benefits of the study are substantial and include potential positive impact on cancer outcomes through improved symptom management, better adherence, and better communication between care teams and patients.

Risk/Benefit Assessment

Although there are potential risks associated with this study, current care and support provided to patients on oral therapies is limited. The lack of medical oversight at home can lead to incorrect dosing and administration of these cytotoxic drugs and in turn potentially hazardous toxicities, underscoring the need for interventions such as the one proposed in this study to help patients. Additionally, we have incorporated protocols to help mitigate potential risks including monitoring of interactions between patients with Penny by clinical research team members and escalation of side effects to the patient's care team.

The potential benefits of this study are great and include the potential to improve adherence and symptom management, improve monitoring of self-based care and decrease unplanned care for cancer patients. If proven to be successful, this study could have a significant positive impact on oncology care across healthcare systems.

10.8 Data Safety and Monitoring

As a phase II behavioral pilot trial, overall data and safety will be monitored on an ongoing basis by the PIs and the study team. As needed, the investigators may decide to appoint an independent medical monitor to evaluate adverse events and make recommendations for continuing or stopping a trial. No interim analysis will be conducted.

Monitoring Text Interactions: The overall framework for monitoring patient-reported data includes notifications to all study team members when a patient sends in a message, with 24-hour check-ins on all new patient interactions from the clinical research team and from Memora Health team members. Given the patient volume, nurse and physician researchers are included in this study for this specific reason. A patient's enrollment in the study will be terminated if they experience an emergency medical situation requiring intervention or violate study protocol.

Adverse Event Reporting: If any breaches in confidentiality or identifying information are identified, the PI will be responsible for jointly notifying the IRB using the eIRB adverse event reporting system within 24 hours. The IC and NIH Office for Biotechnology Activities will additionally be notified within 24 hours via email. Furthermore, all protected health information will be destroyed within five years after study publication. All HIPAA-mandated federal regulations will be followed accordingly.

The probability of adverse events remains extremely low given the nature of this intervention but several safeguards have been built into the protocol to mitigate and monitor any risk due to errors in the text messaging or symptom pathways. First, patients can report all events directly to the study staff or via SMS. Second, all interactions by the chatbot will additionally be monitored by the PI and nurse researchers at a minimum frequency of every 24 hours to ensure escalations are properly routed and any adverse events addressed and recorded. Depending on the nature of the event, the individual's participation in the study may be terminated. In the case of a technical error that results in patients receiving inaccurate information via SMS, the product development team at Memora Health will immediately address the error but enrollment will not be terminated. If the issue cannot be immediately resolved without affecting other patients, the study will be temporarily put on hold until the issue is resolved. In the case of a data leak or HIPAA violation, the study staff and Memora Health team will

jointly address the nature of the leak and determine if any PHI has been leaked. Beyond this, standard HIPAA reporting guidelines will be followed.

Integrity of Study Data: The primary step to maintaining integrity of the data will involve de-anonymization of data prior to any analysis for statistical significance. This is aimed towards reducing any potential risk associated with skewing data based on demographic or personal health information. The care team at the clinical site and the Memora Health team, of which both fall under approved study personnel, will store separate, secure versions of the raw text data in a password-protected file and a secure database, respectively. This will allow for cross-checking between data sets to assure that no data has been modified and no results skewed. Specifically, the clinical PI will oversee the data set on behalf of the clinical site and the care team, while [name] at Memora Health, will oversee the data set on behalf of the Memora Health team.

Adherence to the IRB-approved protocol will be assured by restricting participant enrollment to Penn Medicine research staff who will have conducted the appropriate training, including CITI. Research assistants and staff trained in IRB protocol for study enrollment will participate in enrollment. Additionally, study staff and corresponding research assistants will be briefed on study protocol prior to the beginning of the study to assure that the correct procedure and guidelines are followed.

Mobile Security: Patients will not need to download any mobile app to participate in this study. All study content and expected responses will take place via secure web data form. All of the data both in transit to and from the Memora Health servers, and at rest, will be encrypted. A two-factor authorization approach will be taken at the time of enrollment to maintain confidentiality of patient information. When a patient is first enrolled in the study, they will receive an introductory SMS asking them to verify their identity to assure that messages are being sent to the right individual. Patients are required to opt-in to sending and receiving personal health information over SMS immediately after enrollment in the platform and are instructed on the risks of using SMS as a means of communicating health information. This process complies with both patient privacy and telecommunications laws. Patients will receive regular SMS prompts and personally identifiable health information will be omitted from all text messages, outside of the patient name, to maximize confidentiality on the patient end. Text reminders have patient names in them to assure that the correct person is completing the survey.

Platform Security: Two sets of information, provider login information and patient data, will be confidentially stored to assure that data storage abides by HIPAA regulations. Provider login information is all 192-bit encrypted using bcrypt, a cryptographic algorithm used for file and data encryption purposes. Additionally, provider login passwords, which must be at least eight characters long, are hashed as a second layer of security to protect the identity of providers using the software. Patient data is 256-bit encrypted using Advanced Encryption Standard (AES) while it is being transmitted to the database for storage. Full-disk encryption in a HIPAA-compliant database sponsored by Google Cloud Platform (GCP), a verified cloud data storage location, is used for storage of all information.

Data will be encrypted and stored on GCP as two different sets, personally identifiable (PI) information, such as names and phone numbers, and non-personally identifiable (NPI) information. While PI and NPI information are inherently linked to each other to allow for providers to monitor patients during the course of the study, data can be de-identified by removing PI information. Additionally, this data mechanism storage allows for mitigation of losing any personal health information in the improbable case of a storage leak. When it is necessary, the personally identifiable information will automatically be stripped before being presented to authorized personnel.

All patient data stored by the study staff will be maintained in a password-protected file that contains codes corresponding to a patient's PHI. The code will correlate to a patient's data stored in a separate password-protected file. Ultimately, only authorized study staff will be given login credentials for the platform and therefore controlling the individuals who have access to patient data.

No personally identifiable (PI) information will be shared with anyone outside of the research team, members of the Memora Health team, or patient's care team. Any data shared following completion of the study will be de-identified prior to use, protecting the patients' PHI and abiding by the HIPAA Privacy Rules. The only foreseeable disclosure of data beyond the study is in the case of publication of data.

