5.3 Study Duration

Aim 1: Study enrollment for each participant will last approximately 15-weeks including consent and post-assessment. Observation will begin no earlier than one week after therapy initiation (to allow for a brief prescription run-in period for new starts) and end either 12-weeks later or at therapy discontinuation, whichever is shorter. Post-assessment will occur within 2 weeks after each patient's active observation period. We anticipate the active trial will last approximately nine months, with anticipated enrollment beginning in November-December 2020 and ending in October 2021. Data ascertainment and analyses will continue through December 2021 or later as needed.

Aim 2: Study enrollment for each interview participant will last approximately 60-90 minutes including consent, semi-structured interview, and completion of brief written questionnaire. We anticipate that interviews will begin in December 2020 and continue through November 2021. Analyses will continue through December 2021 or later as needed.

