8.3 Measures

Adherence (Primary Outcome). For each participant, adherence will be calculated based on the overall proportion of adherent days (defined dichotomously based on whether a patient took all prescribed doses for the day within 2 hours of recommended time). Participants who are 95% adherent or above will be classified as adherent (1) and those below will be considered not adherence (0). For therapies that have more than one dose per day, we will also calculate the proportion of doses taken among all prescribed doses. Additionally, we will evaluate persistence as a secondary adherence outcome (defined as the number of consecutive days on the regimen and conversely gaps in overall treatment) to assess how Penny may impact different dimensions of adherence. Adherence will also be assessed via self-report (using a validated visual analog rating scale)^{34,35} and prescription refill orders from the EMR to assess accuracy of self-report and provide contingency measures to support potential, yet unlikely, failures in MEMS caps.³⁶

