9. ANALYSIS PLAN

9.1 Primary Analyses

Our primary analyses will use an intent-to-treat (ITT) approach using repeated measures logistic regression to compare the overall effect of the intervention on patient adherence. We will also explore potential differences in secondary outcomes across arms. Baseline clinical and survey data will be used

to assess potential differences in treatment groups (i.e., socio-demographics and clinical risk factors) using parametric or nonparametric tests as appropriate. Data quality, normality, and other assumptions will be assessed prior to analysis. Using repeated measures logistic regression fitted using generalized estimating equations (GEE), we will compare the proportion of adherent days between Penny and usual care. Data will be treated as binary outcome (0/1) over the study period. Models will contain a predictor term for treatment arm, will be adjusted for time (discrete week), and will contain subject specific random effects and fixed effects for site. Patients will be categorized as adherent (outcome=1) across the study period if the total percentage of adherent days is $\geq 95\%$ similar to previous studies⁷; other percentages (80%, 90%, 100%) will be explored in sensitivity analyses. Persistence will be treated as repeated measure survival data and will be summarized as median survival time using Kaplan-Meier methods. We will also generate summary statistics (including mean adherence rate) to help describe the study population and inform the design of further studies.

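### The termination rule in section 10.8 can be read as ending outcome collection after an emergency or protocol violation, and no available text says follow-up continues

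*Combined protocol and SAP*

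**What the plan says.** Section 10.8, in the paragraph on monitoring text interactions, says that a patient's "enrollment in the study will be terminated if they experience an emergency medical situation requiring intervention or violate study protocol". This is worded as mandatory and is not limited to one arm. Further on, the section covers adverse events in general and says only that, depending on the event, the individual's "participation in the study may be terminated".

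Section 5.3 gives two end points for observation: it will "end either 12-weeks later or at therapy discontinuation, whichever is shorter". It also says: "Study enrollment for each participant will last approximately 15-weeks including consent and post-assessment".

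Sections 4.2 and 5.1 plan to capture adherence in all participants from MEMS caps, surveys and the medical record. Section 5.7 plans to re-contact all patients for the two follow-up surveys. Section 8.2 abstracts medical records for enrolled patients. Section 8.3 uses self-report and refill orders as routine measures and also to "provide contingency measures to support potential, yet unlikely, failures in MEMS caps". It counts emergency room visits and admissions over the study period. Section 9.2 adds passive record follow-up for mortality at 6 and 12 months.

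Section 9.1 states: "Our primary analyses will use an intent-to-treat (ITT) approach using repeated measures logistic regression". It does not say how patients whose enrollment was terminated are handled.

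**The concern.** Both triggers occur after randomisation, and both may be related to what the trial measures. An emergency needing intervention is close to the acute-care counts in section 8.3, so ending follow-up there could cut the count off at its first event. A protocol violation is not defined. Because section 8.2 tells patients to use the cap throughout and to log other openings, failing to do so could be read as a violation, and that behaviour lies close to the primary outcome.

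If termination ends data collection, outcomes are lost for patients whose adherence and acute-care use may differ from the rest. Intention-to-treat keeps them in the analysis set but cannot supply data that were never collected. The 15% loss allowance in section 5.5 protects the number of patients; it does not address selective loss.

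**Working it through.** **1. The texts side by side**

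| Place | What it fixes | After termination |
|---|---|---|
| 10.8, text monitoring | Mandatory end of enrollment for two triggers | Silent |
| 10.8, adverse events | Discretionary end of participation | Silent |
| 5.3 | Observation ends at 12 weeks or therapy stop; enrollment includes post-assessment | Triggers not listed |
| 4.2, 5.1, 5.7 | Caps, surveys and records for all participants | Silent |
| 8.2 | Records of enrolled patients | Silent |
| 8.3 | Self-report and refill orders, routine and as back-up | Silent |
| 9.1 | Intention-to-treat | Silent |
| 9.2 | Passive mortality follow-up | Silent |

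Since section 5.3 counts post-assessment as part of enrollment and section 8.2 ties record abstraction to enrolled patients, ending enrollment can be read as ending both.

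**2. The plan's own figures**

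Section 5.5 gives 170 patients, 15% loss, 72 per arm, 65.5% adherent in controls, a 20.9-point difference and Fisher's exact test. 170 × 0.85 = 144.5, or about 72 per arm. Exact enumeration of Fisher's test for 65.5% versus 86.4% with 72 per arm gives power 0.800 (two-sided 5% assumed, since no alpha is stated). The plan's figure reproduces, and the sample size is not in question here.

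**3. Illustration of size**

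From the plan: 65.5% adherent, taken in both arms so that there is no true effect. Assumed, because the documents give no figures: the share removed, e, and the adherence p that removed patients would have shown if followed, set at 40% or 30%. These are selected examples, not a range.

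(a) Removed patients wholly excluded: rate = (0.655 − e·p)/(1 − e).

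| e | p = 0.40 | p = 0.30 |
|---|---|---|
| 0 | 65.50% | 65.50% |
| 2.5% | 66.15% | 66.41% |
| 5% | 66.84% | 67.37% |
| 15% | 70.00% | 71.76% |

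(b) Removed patients counted as not adherent: rate = 0.655 − e·p. For example, e = 15% and p = 0.40 gives 0.655 − 0.060 = 59.5%.

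Difference in points, arm with more removals minus the other (p = 0.40 / 0.30):

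| Removed | (a) Excluded | (b) Not adherent |
|---|---|---|
| 5% vs 2.5% | +0.69 / +0.96 | −1.00 / −0.75 |
| 15% vs 5% | +3.16 / +4.40 | −4.00 / −3.00 |
| 15% vs 0% | +4.50 / +6.26 | −6.00 / −4.50 |

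(c) Removed patients followed to the end: 65.5% in both arms, difference 0. Equal removal with equal p also gives 0 under (a) and (b).

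The plan states neither (a) nor (b). Keeping the weeks before termination in the section 9.1 model would give other figures, which were not computed.

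**The case against.** The strongest reply is that the sentence closes a paragraph about text messages and may mean only that the chatbot stops. Section 10.8 also speaks of enrollment in the messaging platform and says that enrollment is not ended by a technical messaging error. This reading is possible. Against it stand the reference to the study in the sentence itself and the use of the term in sections 5.3 and 8.2. The text is ambiguous, and one sentence would settle it.

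A reader might infer that the sections contradict each other. They do not have to: section 5.3 can be read as a planned duration, and the mandatory rule as a specific case of the discretionary one. The plan does not say so, which leaves them unreconciled.

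A reader might also infer that adherence has no other source once the cap is lost. That is not supported, since section 8.3 uses self-report and refill orders routinely and sections 4.2, 5.1 and 5.7 speak of all participants or patients. What stands is that none of this text mentions terminated patients.

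Nor do the documents show that removals would favour either arm. Chatbot interactions are "monitored by the PI and nurse researchers at a minimum frequency of every 24 hours", which could reveal more triggers in the Penny arm. But "patients can report all events directly to the study staff or via SMS", and records and self-reported visits are not limited to one arm. Differential detection is a possibility only.

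Finally, section 10.8 calls adverse events very unlikely, and a terminated patient could still contribute the days already observed. Both points argue for a small effect, and neither says what happens after termination.

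**Conclusion.** The point holds as an ambiguity with a real consequence. On a well-supported reading, the rule stops outcome collection selectively after post-randomisation events, and nothing available says otherwise. This rests on the text that could be read: the part between sections 9.3 and 10.2 and the consent form were not available, and section 9.2 points to the consent form for passive record data.

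The size is unknown. Under the assumptions above, the shift is about 1 point with few removals and up to about 6 points with very unequal ones, against a planned detectable difference of 20.9 points. Its direction depends on a handling choice that the plan does not state, and it is zero if removed patients are followed. It would go too far to conclude that the plan excludes these patients from the primary analysis or that the result will be biased. This is a cheap improvement worth making, not a flaw that invalidates the design.

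**What to change.** Reconcile section 5.3 with the two statements in section 10.8 by separating the end of chatbot messaging from the end of data collection:

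- State that termination under section 10.8 ends messaging and not outcome collection.
- In both arms, continue cap, survey and medical-record acute-care collection to the end of the section 5.3 observation period and through the planned post-assessment, unless the patient withdraws consent.
- State in section 9.1 that every randomised patient stays in the assigned arm.
- Report terminations by arm and reason.

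When messaging stops is left to the investigators.

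The cost is protocol and analysis-plan wording, a check that the consent text covers continued collection, and modest follow-up effort. The affected patients must keep using the cap, and staff must scan it and chase surveys. The collection systems already exist in both arms.

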12. APPENDICES
